### 6.7 Analysis plan

Data collected will be verified before analysis, which will be done with Data Analysis and Statistical Software: STATA, version 13 with an alpha of 0.05 set a priori. All participants will be followed up for two weeks and we will summarize their baseline demographic and technology use characteristics.

To address the primary aim, the feasibility success rate will be calculated as the number of evaluable patients who meet the criteria for 'success' (per section 6.1) divided by the total number of evaluable patients. A 95% confidence interval will be calculated on this proportion. If the upper limit of the 95% confidence interval is less than 80%, then we will consider the iThermonitor not to be a feasible clinical decision support tool.

Descriptive analyses will be performed on all baseline data. Endpoints for all study outcomes are defined in section 6.1 above. All continuous variables will be computed as means with standard deviations, median and ranges while categorical variables will be computed as frequency distributions and percentages. The binomial test of proportion will be used to our dichotomous outcome of successfully using the iThermonitor. Paired t-test will be used to

analyze pre- and post- GAD-7 scores measured as a continuous variable. All other outcome variables will be summarized with descriptive statistics.

#### 6.8 Handling of missing data in the analysis

We have adopted simple data collection techniques to limit missing data for this trial. Since this is largely exploratory work with descriptive statistics, a complete case analysis approach will be adopted for this study. .

### Section 3 510(k) Summary

This 510(k) Summary of 510(k) safety and effectiveness information is being submitted in accordance with requirements of 21 CFR-Section 312.92.

The assigned 510(k) Number: K132761

1. Prepared Date: Aug. 26, 2013

#### 3. Submission Correspondent

**[name]**

**Title: General Engineer**

**Email: [contact]**

[contact]

[contact] ext. 776445

Raiing Medical Company  
[name]

4. Proposed Device Identification

Proposed Device Name: Wireless Thermometer  
Proposed Device Common Name: Thermometer

Regulatory Information:

Classification Name: Clinical Electronic Thermometer;  
Classification: II;  
Product Code: FLL;  
Regulation Number: 21 CFR 880.2910;  
Review Panel: General Hospital;

Intended Use Statement:

The Wireless Thermometer is a battery-operated electronic device with intended use of measuring and monitoring human armpit temperature continuously via wireless signal transmission of the measuring result. This system is reusable and intended for armpit temperature monitoring for persons over two years old.

5. Predicate Device Identification

510(k) Number: K121696  
Predicate Device Name: Wireless Thermometer WTM-BT30-1  
Manufacturer: Raling Medical Company

6. Device Description

The wireless thermometer, WT701, which is the combination device of thermometer and Bluetooth communication unit intended to be worn at axilla to monitor the armpit temperature continuously.

For the monitoring operation, switch the thermometer on and stick the thermometer in the user's axilla. The thermometer will make a Bluetooth connection between the thermometer and the receiver automatically (User should setup Bluetooth properly on receiver). Then the thermometer starts to measure the body temperature by means of testing the NTC resistor's resistance value and calculates the body temperature every 4 seconds continuously and sends the temperature data to the receiver through

**Bluetooth connection.**

The wireless thermometer uses a CR2032 battery for operation. When the battery is low, internal circuit will detect the low battery condition automatically and send "low battery" signal through Bluetooth communication unit to receiver.

7. Non-Clinical Test Conclusion

**Non-clinical tests were conducted to verify that the proposed device met all design specifications as was Substantially Equivalent (SE) to the predicate device. The test results demonstrated that the proposed device complies with the following standards:**

IEC60601-1:2005 Medical electrical equipment Part 1: General requirements for basic safety and essential performance

IEC 60601-1-2:2007 Medical electrical equipment- Part 1-2: General requirements for basic safety and essential performance- Collateral standard: Electromagnetic compatibility- Requirements and tests

FCC Part 15 Subpart C test FCC Part 15.247

ASTM E1112-00: 2006 Standard Specification for Electronic Thermometer for Intermittent Determination of Patient Temperature.

EN 12470-4: 2000+AI:2009 Clinical thermometers Part-4: performance of electrical thermometers for continuous measurement.

And the proposed device also conducted the performance test, which include Dimension Test, Weight Test, and accuracy transmission test under a complex electromagnetic environment.

8. Substantially Equivalent (SE) Conclusion

**The following table compares the DEVICE to the predicate device with respect to intended use, technological characteristics and principles of operation, etc.**

Table 3-1 Comparison of Technology Characteristics

ITEM	Proposed Device WT701	Predicate Device K121696
Product Code	FLL	FLL
Regulation No.	880.2910	880.2910
Class	Class II	Class II

Intended Use	The Wireless Thermometer is a battery-operated electronic device with intended use of measuring and monitoring human armpit temperature continuously via wireless signal transmission of the measuring result. This system is reusable and intended for armpit temperature monitoring for persons over two years old.	The Wireless Thennometer , model WTM-B530-J, is a battery-operated electronic device with intended use of measuring and monitoring human armpit temperature continuously via wireless signal transmission of the measuring result. This system is reusable and is intended for armpit temperature monitoring for persons over two years old.

If your device is classified (see above) into either class II (Special Controls) or class III (PMA), it may be subject to additional controls. Existing major regulations affecting your device can be found in the Code of Federal Regulations, Title 21, Parts 800 to 898. In addition, FDA may publish further announcements concerning your device in the federal Register.

Please be advised that FDA's issuance of a substantial equivalence determination does not mean that FDA has made a determination that your device complies with other requirements of the Act or any Federal statutes and regulations administered by other Federal agencies. You must comply with all the Act's requirements, including, but not limited to: registration and listing (21 CFR Part 807); labeling (21 CFR Part 801); medical device reporting (reporting of medical device-related adverse events) (21 CFR 803); good manufacturing practice requirements as set forth in the quality systems (QS) regulation (21 CFR Part 820); and if applicable, the electronic product radiation control provisions (Sections 531-542 of the Act); 21 CFR 1000-1050.

If you desire specific advice for your device on our labeling regulation (21 CFR Part 801), please contact the Division of Industry and Consumer Education at its toll-free number [contact] or [contact] or at its Internet address <http://www.fda.gov/MedicalDevices/ResourcesforYou/Industry/default.htm>. Also, please note the regulation entitled, "Misbranding by reference to premarket notification" (21 CFR Part 807.97). For questions regarding the reporting of adverse events under the MDR regulation (21 CFR Part 803), please go to <http://www.fda.gov/MedicalDevices/Safety/ReportaProblem/default.htm> for the CDRH's Office of Surveillance and Biometrics/Division of Postmarket Surveillance.

You may obtain other general information on your responsibilities under the Act from the Division of Industry and Consumer Education at its toll-free number [contact] or [contact] or at its Internet address <http://www.fda.gov/MedicalDevices/ResourcesforYou/Industry/default.htm>.

Sincerely yours,

## Indications for Use

510(k) Number (if known)  
KJ32761

Device Name  
Wireless Thermometer, Model WT701

### Indications for Use (Describe)

The Wireless Thermometer is a battery-operated electronic device with intended use of measuring and monitoring human armpit temperature continuously via wireless signal transmission of the measuring result. This system is reusable and intended for armpit temperature monitoring for persons over two years old.

Type of Use (Select one or both, as applicable)

Prescription Use (Part 21 CFR 801 Subpart D)       Over-The-Counter Use (21 CFR 801 Subpart C)

PLEASE DO NOT WRITE BELOW THIS LINE- CONTINUE ON A SEPARATE PAGE IF NEEDED.

FOR FDA USE ONLY

Concurrence of Center for Devices and Radiological Health (CDRH) (Signature)

Digitally signed by [name] -S  
Date: 2014.07.08 11:26:01 -04'00'

This section applies only to requirements of the Paperwork Reduction Act of 1995.

**\*DO NOT SEND YOUR COMPLETED FORM TO THE PRA STAFF EMAIL ADDRESS BELOW.\***

The burden time for this collection of information is estimated to average 79 hours per response, including the time to review instructions, search existing data sources, gather and maintain the data needed and complete and review the collection of information. Send comments regarding this burden estimate or any other aspect of this information collection, including suggestions for reducing this burden, to:

[figure not shown]
Department of Health and Human Services  
Food and Drug Administration  
Office of Chief Information Officer  
Paperwork Reduction Act (PRA) Staff  
[[contact]](mailto:[contact])

*"An agency may not conduct or sponsor, and a person is not required to respond to, a collection of information unless it displays a currently valid OMB number."*

## Section 9 Biocompatibility

### 1. Patient--Contact Material Identification

The patient--contact components and materials are presented as follows:

Table 9--1 Patient Contact Material Identification

Components	Material	Contact Level	Contact Duration
Double coated medical tape	Medical Tape	Surface	Short-term (<24h)
Shell	ABS	Surface	Short-term (<24h)

*NOTE: The contact level and contact duration are determined according to Annex A of ISO 10993--1:2009 Biological evaluation of medical devices — Part 1 Evaluation and testing within a risk management process.*

### 2. Biocompatibility

The patient contact material(s) of the proposed device as identified is(are) identical device to that(those) of the legally marketed device, wireless thermometer , as cleared in K121696 at date Oct. 11, 2012. Biocompatibility Statement is provided in Exhibit #8 Biocompatibility Statement.

May 23, 2012

Dear Valued 3M Customer:

This letter is in response to your request for composition information on the products listed below.

You requested information regarding the following 3M products:

3M™ Spunlace Nonwoven Tape 2476 and 2476P

3M Skin and Wound Care Division does not add animal derived materials or tissues to these products during manufacture. We are not aware that the suppliers for the ingredients used to make these products add or use animal derived materials or tissues during their operations. Since the products do not contain any animal derived material they are compliant with US and EU regulations for Bovine Spongiform Encephalopathy (BSE) or Transmissible Spongiform Encephalopathy (TSE) control.

This information was prepared based on the best knowledge and understanding of the Skin and Wound Care Division and, in part, on other information provided by 3M suppliers.

In the event any product listed above is proven not to conform with 3M's certification, then to the extent permitted by law, 3M's entire liability and Buyer's exclusive remedy, will be at 3M's option either: (i) replacement of Product with a conforming product, or (ii) refund of the purchase price paid by Buyer for each non-conforming Product, within a reasonable time after written notification of said non-conformance and return of said Product to 3M. 3M shall not under any circumstances be liable for direct, incidental, special, or consequential damages (including but not limited to loss of profits, revenue, or business) related to or arising out of this certification, including, the use, misuse or inability to use the Product. Unless stated otherwise in writing, the foregoing language cannot be waived, modified, or supplemented in any manner whatsoever.

If you have other related questions or need further information you may contact me at [contact].

Sincerely,

A handwritten signature in black ink that reads "[name]". The signature is written in a cursive style and is placed above the typed name and contact information.

[name]  
3M Skin and Wound Care Division  
Product Responsibility  
3M Company  
[name]  

**Preliminary Technical Information Sheet**

**Product Number #2476P** [formerly MSX-6935B]

**3M™ Single Coated Nonwoven Medical Silicone Adhesive Tape on Premium Liner**

Effective: March 2013

Supersedes all previous versions

**Proposed Features and Benefits:**

- Hypoallergenic Silicone Pressure Sensitive Adhesive
- Flexible, Conformable
- Excellent Initial Skin Adhesion
- No Natural Rubber Latex
- EtO Sterilization Compatible Only
- Premium Clear Polypropylene Liner

**Current Composition:**

Tape Caliper	14.6 mil [0.37 mm] single-coated Film Tape on Clear Polyester Liner
Backing	10.6 mil [0.27 mm] White Polyester Spunlace Nonwoven/Film Laminate
Adhesive	4 mil [0.10 mm] Medical Grade Gentle 3M Silicone Adhesive
Release Liner	3.5 mil [0.09mm] Clear Polypropylene Film, one side Fluoropolymer Release

**Preliminary Properties+:**

Adhesion to Stainless Steel, 180q Peel	4.5 oz/inch [128 gms/25.4 mm] [1.25 N/25.4 mm]
Typical Liner Release, 180q Peel	10 gm/inch width [10 gms/25.4 mm width]
Moisture Vapor Transmission Rate, MVTR	800 gms/sq m/24hrs

+ 3M test methods are available upon request.

1 Preliminary results based on limited run data. Subject to change.

**Proposed Roll Description:** Tape supplied on 3 inch (76 mm) diameter cores.

Length, Maximum	100 yds [91.4 meters]
Width, Maximum	12 inches (30.5 cm)

**Packaging and Recommended Storage:**

Product as supplied in original packaging will maintain stated properties for a period of two years from date stamped on shipping container when stored at temperatures of 50-80qF (10-27qC) and relative humidity between 40-60 percent.

**Note:** Product should be stored in the original packaging out of direct sunlight or high-intensity indoor lighting.

**Please see reverse side for important product, safety and warranty information.**

**Product and Safety Information:** User is solely responsible for determining the suitability of 3M samples and products for the intended use including any necessary safety or toxicity assessment. 3M will provide Material Safety Data Sheets and results of toxicity testing upon request. In every case before using any product in full scale production users should conduct their own tests to determine to their own satisfaction whether the product is of acceptable quality and is suitable for their particular purposes under their own operating conditions.

**Notice:** Nothing contained herein shall be construed to imply the nonexistence of any relevant patents or to constitute a permission, inducement or recommendations to practice any invention covered by any patent, without authority from the owners of this patent.

#### Warranty Information

All statements, technical information and recommendations herein are based on tests 3M believes to be reliable, but the accuracy or completeness thereof is not guaranteed. 3M warrants only that products will meet 3M's specifications at the time of shipment to the customer. 3M does not offer any other warranty and does not warrant the performance, safety or such other characteristics of Products in combination with other materials. 3M specifically DOES NOT warrant Products for any intended or unintended uses (whether or not foreseeable); for compatibility or suitability with other components or compatibility with any methods of manufacture or conversion. The foregoing warranty is made in lieu of all other warranties, expressed or implied, including the implied warranties of merchantability, fitness for a particular purpose and freedom from non-infringement.

**Limitation of Remedies:** If products are proven not to meet 3M's specifications, the sole and exclusive remedy available and 3M's only obligation shall be, at 3M's option, to replace such quantity of Products which are proven out of specification or to refund the purchase price paid for Products.

**Limitations of Liabilities:** The remedies provided herein are exclusive remedies against 3M for any alleged or actual nonconformance to specifications or defect or other failure in products or for 3M's performance of its supply obligations. Under no circumstances is 3M liable for any direct, indirect, incidental, special or consequential damages (including lost profits) in any way related to the product under any theory of law including, but not limited to, negligence and strict liability.

# TECHNICAL SPECIFICATIONS

---

## Product name

Wireless Thermometer

## Valid transmission distance

Up to 5 meters

## Model

WT701

## Temperature unit

°C or °F

## Size

51.9mmx31.6mmx6.5mm

## Measurement range

25'(-45'(

## Weight

6g (without battery)

## Accuracy

±0.05°C (35°C-38.5°C)

±0.1°C (25°C-34.99°C and 38.5°C-45°C)

## Battery

CR2025

## Receiver

iPhone 4s+, iPad 3+,  
iPad mini+, iPad Air, iPod touch 5+

Android Devices

(with 4.3+ system and Bluetooth 4.0; for more details  
about Android support, please see our website)

## Battery life

120 days at 8 hours per day

Note: frequent synchronization of data  
may deplete power more quickly

## Operating conditions

Temperature: 5°C - 40°C

Humidity: 15% - 85%

Barometric pressure: 86kPa - 106kPa

[figure not shown]

## iThermometer Instruction Guide

### Preparation of the iThermometer

- Remove the cover of the patch. The patch is the sticky adhesive.
- Face the temperature sensor up and stick the other side with the button to the patch. Make sure the device is in the center of the sticker.
- The iThermometer should be aligned vertically with the patch

[figure not shown]
### Wearing the iThermometer

- Lift the child's arm naturally.
- Paste the device facing vertically into the armpit. Try to get the device as close to the most inner part of the armpit.
- Make sure that the device is laying flat and smooth against the skin

#### 5 Wearing

Step 1. Lift the arm naturally.

Step 2. P

Note: An adult should help children wear and operate the device, to ensure the area of skin it is in contact with stays flat and smooth.

Note: To avoid disconnections, please make sure device and receiver are on the same side of your chest when wearing the device.

[figure not shown]
- If the connection is lost, the sensor will continue recording and storing temperature data for maximum 10 days. The data will be automatically synced with iPad once the connection is back.

[figure not shown]
## Changing the battery

Your device will come with a battery installed. This battery should last throughout the two-week study. If you believe the battery has died, please follow the instructions below to install the replacement battery, which was given to you at enrollment.

- Use the battery tool and rotate clockwise to open.
- Remove the old battery.
- Insert the new battery (+) side up.
- Replace battery cover and rotate counterclockwise to close.

Use battery tool to open for further use.

If you want to download on your own iOS device, please use the following link:

<http://doc.raing.com/enterprise/mgh.html>

## Using and maintaining the iThermonitor

- Charge the iPad regularly and keep the iThermonitor app open. Do not log out of the app.
- Make sure the Bluetooth is in the on position.
  - If you have a Wi-Fi connection in your home, connect the iPad to the Wi-Fi to allow the iThermonitor to sync for data collection.
- DO NOT change settings of the iPad or the iThermonitor app.
- DO NOT get the iThermonitor wet (shower, bath swimming, etc).
- DO NOT wear the iThermonitor at one side for more than 24 consecutive hours. Change sides everyday to wear it for continuous monitoring.
- If your child feels unwell (uncomfortable or allergic) when using the patch, replace it with another type of adhesive dressing based on your doctor's advice. A fully-covered patch larger than 76mm×62mm should be used.
- Do not reuse the patches. If a patch is already folded over, a new patch is required.

Appendix 1.4 User Manual – to be sent home with subjects

- Shave armpits in advance. Make sure the area of skin in contact with the patch is flat and smooth.
- For the most accurate results, make sure the iThermonitor has been at room temperature for at least 5 minutes before using it.

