Neutropenia predisposes patients to significant risk for infectious complications which increases morbidity and mortality. Usually, fever is the first clinical sign of the inflammatory response to the infective process; and early detection is an indication for empiric antimicrobial therapy and further evaluation to determine risk for sepsis. Today, broad-spectrum antimicrobial therapy at the first detection of fever has helped significantly decrease the mortality associated with neutropenia in the intensive phase of chemotherapy. Therefore, early detection of fever, through regular temperature monitoring, in a neutropenic patient is critical to improved clinical outcome. Vigilance on the part of care providers and caregivers is crucial to early detection. Traditionally, this is simply done through episodic oral or axillary monitoring of temperature. In this study, we propose to test the use feasibility of an innovative device that continuously monitors body temperature as a clinical decision support tool in pediatric patients undergoing myelosuppressive therapies for acute leukemias and other childhood cancers.

The iThermonitor, a FDA class II device, is a high accuracy device that continuously captures body temperature and automatically delivers the data wirelessly (via blue tooth or wi-

fi) to mobile devices or for cloud storage. It has the capacity to store 10 days worth of recorded temperature data. The device can be used to effortlessly monitor patients on a continuous basis during the intensive phase of chemotherapy as opposed to the usual episodic oral or axillary measurements. It is also able to generate and deliver out-of-range temperature alerts on a mobile application for care givers or providers. It also provides care providers an opportunity to remotely monitor their patients' temperature in the immediate period after discharge from the hospital. Therefore, we hypothesize that the iThermonitor can serve as a feasible clinical decision support in the management of pediatric patients undergoing intensive treatments for acute leukemia and other childhood cancers. The device hasn't been previously tested for use in pediatric patients and finding from this study could generate useful data for future studies.

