#### 3.1a Inclusion criteria - Child:

- Pediatrics patients aged 2-17 years undergoing myelosuppressive therapies for acute leukemias and other childhood cancers.
- If applicable, willingness of the patient to shave axillary (armpit) hair.
- Ability of patient (if old enough) to read and speak English
- Has a caregiver,  $\geq 18$  years of age that is willing to participate in the study

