### 3.1b Justification of inclusion criteria:

- The iThermonitor is recommended for use only in children aged 2 years and above.
- Shaving is recommended for older children who have attained puberty because the device works best when in contact with flat and smooth skin.
- Participation of caregivers is needed because they will be required to monitor temperature data on the provided iPad mini and also to help answer questions pertaining to the usability of the iThermonitor.
- Fluency in English is required because the study materials will be administered only in English.
- No study procedure will be performed without informed consent from the parents or legal guardians of patients.

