Caregivers who have smartphones can also view their children’s temperature data on their personal smartphones (in addition to the iPad mini provided) if they wish. To be able to view temperature data on their smartphones, caregivers will have to download the iThermonitor from the Apple App and Google Play stores. The iThermonitor app is available for iPhone and Android users and there is no cost to downloading it on their phones. User manuals to guide use will be given to all subjects. (Appendices 1.4,)

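### The take-home manual tells every family to shave the child's armpits, without the condition that the protocol attaches to shaving

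*Combined protocol and SAP*

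**What the plan says.** Section 3.1a lists as an inclusion criterion for the child: "If applicable, willingness of the patient to shave axillary (armpit) hair". The letter to oncologists (Appendix 2.1) and item 4 of the eligibility checklist (Appendix 5.1) use the same conditional wording. The justification in section 3.1b gives the reason and says whom it concerns: "Shaving is recommended for older children who have attained puberty because the device works best when in contact with flat and smooth skin".

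The enrolled population is wider than that group: "Pediatrics patients aged 2-17 years undergoing myelosuppressive therapies for acute leukemias and other childhood cancers".

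The user manual (Appendix 1.4) is marked "to be sent home with subjects", and section 5.3 states "User manuals to guide use will be given to all subjects". Its line on shaving reads "Shave armpits in advance. Make sure the area of skin in contact with the patch is flat and smooth". It mentions neither age nor puberty, and does not say that the line applies only to some children.

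**The concern.** The device is worn only at home (section 5.1), and section 5.66 relies on the manual to guide set-up and use after enrollment. The manual is therefore the text that families act on. The inclusion criterion, its justification, the checklist and the oncologist letter are read by staff and physicians. The condition on shaving appears in all four of those and is missing from the one sheet that reaches the home.

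Screening and instruction also fail to match. Willingness to shave is an eligibility question only where shaving applies. A family for whom it did not apply may never have been asked, yet is later told to shave.

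The population makes the line worth correcting. Section 1.2 says "Neutropenia predisposes patients to significant risk for infectious complications which increases morbidity and mortality", and section 3.1d excludes hydrogel allergy and skin disease to limit skin reactions. The manual also has families change the wearing side every day and use each patch only once, so the instruction concerns both armpits, each then covered by a fresh adhesive. What is at stake is a participant-facing instruction that goes further than the protocol does, in children whom the protocol itself treats as vulnerable to infection.

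**Working it through.** No figure in the plan bears on this point and no formula applies. The check is a comparison of the places that mention shaving, followed by a search for any text that would correct the manual.

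**Step 1: each statement on shaving.**

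| Place | Reader | Condition on who shaves |
|---|---|---|
| Section 3.1a, inclusion criterion | Study staff | Yes: only where it applies |
| Section 3.1b, justification of inclusion criteria | Study staff | Yes: "Shaving is recommended for older children who have attained puberty" |
| Appendix 2.1, letter to oncologists | Referring physicians | Yes: same wording as 3.1a |
| Appendix 5.1, checklist item 4 | Research assistant | Yes: same wording as 3.1a |
| Appendix 1.4, user manual | Every family | None |

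Four places carry a condition and agree with one another. The fifth does not carry it.

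**Step 2: who receives the unconditional line.** By section 5.3 every subject receives the manual. Enrollment starts at age 2, so recipients include families of children who have not attained puberty.

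**Step 3: is the line corrected elsewhere?** Section 5.61 has the research assistant explain and demonstrate the device, and section 5.66 makes staff available for questions. Neither mentions shaving. Nothing else in the available text tells a family that the line may not concern their child.

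**Step 4: do the purposes differ?** No. The manual and section 3.1b give the same reason, good contact with even skin. They differ only in whom the advice addresses.

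**Step 5: does it reach the statistics?** The primary endpoint (section 6.1) is whether temperature data could be viewed on the iPad mini on at least 80% of days. The sample size (section 6.2) rests on the precision of that proportion with 25 evaluable patients, and section 6.7 analyses that proportion. None of these depends on who shaves.

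**The case against.** The strongest reply is that this is a missing qualifier and not a pair of opposed rules. Section 3.1b makes a recommendation and section 3.1a sets a condition; neither forbids shaving in other children. A reader might infer that the protocol confines shaving to children past puberty, or that shaving a younger child serves no purpose known to the protocol. The text supports neither reading, since no prohibition exists and the manual states the same purpose as section 3.1b. This stands.

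It is also fair to say that a child without axillary hair has nothing to shave, that many families would pass over the line, and that a research assistant holding the conditional checklist meets each family in person. The documents give no information on how families would act. They also name no risk from shaving. The silence of section 5.5 proves little, because the reaction to the adhesive is likewise absent there and appears in section 5.7. The consent form and parts of the parent phone script were not available for this review and may contain a qualifier. All of this lowers the severity. A qualifier in the consent form would still leave the manual at odds with sections 3.1a and 3.1b.

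Two further inferences are tempting. One is that irritation from shaving would be charged to the patch and distort the tolerability or wear results. The documents do not show this: no endpoint is called tolerability, the daily log records only whether the device stayed on and whether data could be viewed, and section 5.71 requires a causality judgment for each adverse event.

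The other is a count of affected children. With ages assumed even over the 16 single years from 2 to 17, and an assumed pubertal cut-off between 10 and 13, the share below the cut-off runs from 8/16 = 50% to 11/16 = 69%, or about 12 to 17 of 25. Neither assumption comes from the documents, and the result counts recipients of a sentence, not children shaved or harmed. It should not be used as a measure of harm.

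**Conclusion.** The inconsistency is real and of low severity. The manual gives all 25 families an unconditional instruction to shave, where four other places in the protocol package attach a condition. Read literally, it directs families of younger myelosuppressed children to a skin procedure that the protocol does not call for in them.

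The conclusion rests on the wording of the available documents and on the manual being used as sections 5.3 and 5.66 describe. It does not rest on any assumption that families would comply or that harm would follow. How many children would be affected in practice cannot be determined from the documents. It is a participant-safety wording point with no statistical consequence.

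**What to change.** Reconcile the shaving line in Appendix 1.4 with sections 3.1a and 3.1b, so that the manual carries the same condition on who is to shave as the rest of the protocol package. The clinical team sets that condition; this review takes no position on what it should be. The oncologist letter and checklist item 4 already match section 3.1a and need a change only if the team rewords the condition. Having the research assistant mark on each manual whether the line applies to that child is optional.

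The cost is a few words in one appendix before the manual is handed out. Sample size, data collection and analysis do not change.
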